9.9.3. Sensitivity Analysis

Due to early termination of the study enrollment, assessing the robustness of the primary analysis will be performed by evaluating the primary endpoint using the per-protocol population.

9.9.4. Subgroup Analyses

Subgroup analysis of the primary functional endpoint of patency will be performed using a logistic regression model to determine if there are significant differences in the patency rates between:

- Subjects with unilateral vs. bilateral renal stenosis
- Gender
- Age (<=45 or > 45 years old)

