5.2 Discussion of Endpoint Determination

The primary functional endpoint of primary patency has been established since the clinical care

Amendment #1: 15Jul13

Confidential

of the physician is considered a more objective measurement of stent performance than the restenosis measurement of DUS alone. In standard practice, a DUS is used to determine patency of a stent. If a DUS is negative and the subject is asymptomatic, no intervention is typically conducted by a physician. If a subject is symptomatic or a DUS is positive, a confirmatory angiogram is typically performed to assess the patency of the vessel.

To properly match the functional outcomes with historical data, the endpoint will be calculated on a per lesion basis. This reflects the current standard of care of treating subjects with single vessel renal artery lesions and those subjects with bilateral renal artery stenosis. Analysis of past studies has demonstrated that the number of lesions treated per subject has increased with time. A recent renal trial reported 1.2 lesions per subject were treated.

The primary clinical endpoint of reduction in SBP has been established to determine the benefit of revascularization therapy to perfuse the kidney. The Framingham Heart Study showed that decreasing SBP by 10mmHg can be lifesaving. Additionally, Joint National Committee VII (JNC VII) estimates that a 5mmHg reduction in SBP would reduce the incidence of stroke in subjects by 14%, coronary heart disease (CHD) by 9%, and overall mortality by 7%. JNC VII also presented data from a UK diabetes study that demonstrated a 10mmHg decrease in SBP was associated with average reductions of 15% for diabetes-related mortality, 11% for MI, and 13% for microvascular complications of retinopathy or nephropathy.

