6. CHANGES IN THE CONDUCT OF THE STUDY OR PLANNED ANALYSES

6.1 Changes in the Conduct of the Study

The enrollment for Protocol/CIP No. iCAST™ RX-ARAS-001 has been terminated after 68 subjects were screened and enrolled in the study as of November 2017. Enrolled subjects will be followed up to study completion.

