7.6 Endpoints, Safety Outcomes and Other Parameters

7.6.1.Primary Endpoints

Primary Patency Rate

In order to mitigate the challenges with DUS interpretation, clinical validation through independent noninvasive core laboratory and/or angiography will be performed in order to correctly validate and definitively assess percent diameter stenosis. DUS is highly reliable in identifying widely patent stents – however, correlation studies of DUS with angiography have confirmed that DUS is not as accurate when results suggest a stenosis. To lessen the risk of inaccurate readings, if a stenosis is detected in DUS (RAS > 60%) or if the DUS is non-diagnostic due to an imaging quality problem then a contrast angiogram will be used to assess the degree of restenosis of the covered stent(s) at the 9-month visit (± 30 days).

The primary efficacy variable is the primary patency rate, defined as continuous patency without the occurrence of a total occlusion (complete obstruction or a closure of a passageway or vessel determined by DUS or contrast angiogram) of the original lesion, and

Amendment #1: 15Jul13

Confidential

- without a re-intervention due to a clinically driven restenosis or occlusion to treat a partial or total occlusion of the stented segment,
- or bypass of the stented segment due to clinically-driven restenosis or occlusion

The primary patency will be calculated on a per lesion basis – for purpose of analysis in cases in which multiple lesions are covered by one stent then the stented segment will be considered as one lesion. The cumulative incidence of patency at 9 months will be computed as the number of lesions that met primary patency divided by the number of subject-lesions for the population being analyzed.

Change from Baseline in Systolic Blood Pressure

Systolic blood pressure will be assessed at each follow-up study visit. Blood pressure measurements will be obtained with a certified, calibrated, and validated equipment. Subjects will be instructed to refrain from exercise, smoking or caffeine ingestion for 30 minutes before blood pressure measurement, and measurements will be obtained after at least 5 minutes of rest. At each time point, a minimum of three (3) readings separated by 2 minutes will be averaged.

The primary clinical outcome is the improvement in systolic blood pressure (SBP) at 9-months as compared to baseline systolic blood pressure computed as follows:

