8.8 Unit of Analysis

For the primary functional endpoint of primary patency rate the unit of analysis is the atherosclerotic lesion(s). The rationale for analyzing the primary endpoint following a per lesion approach, is to avoid overestimation of the failure rate, as more lesions would be at risk for restenosis but would not be accounted for in a per subject analysis.

Since blood pressure is measured on the subject level, the primary clinical endpoint of change SBP will be evaluated at the subject level.

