9.9.1. Primary Patency Analysis

The primary endpoint will be the cumulative incidence of primary patency at 9-months of study computed as the number of subjects with primary patency at 9-months divided by the number of subjects in the ITT population. An exact binomial one-sided 95% confidence interval will be constructed and the upper limit compared to the Performance Goal equal to 70%. A p-value for the one-sided exact test of the difference between the observed rate and the Performance Goal will be presented. The primary analysis will be analyzed with observed data only.

A planned subgroup analysis of the primary functional endpoint will be performed (details are provided in section 9.9.4

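### If the lesion is the unit, the SAP 9.9.4 subgroup model makes no allowance for two lesions in one subject, and a subgroup may have too few failures for a stable odds ratio

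*SAP*

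**What the plan says.** SAP 9.9.4 plans a subgroup analysis of patency "performed using a logistic regression model to determine if there are significant differences" by unilateral versus bilateral stenosis, gender, and age split at 45 years. It does not say whether a record is a lesion or a subject. It gives no correlation structure, variance method or fallback for sparse data, and neither document supplies one elsewhere.

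The SAP defines the unit of patency in two ways:

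- SAP 7.6.1 takes the "number of lesions that met primary patency divided by the number of subject-lesions for the population being analyzed", and SAP 8.8 also names the lesion as the unit for this endpoint.
- SAP 9.9.1 takes the "number of subjects with primary patency at 9-months divided by the number of subjects in the ITT population".

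SAP 8.1 adds a one-sided exact 95% interval for the patency rate in each subgroup. It refers the reader to a section 8.9.4, which does not exist; the subgroup section is 9.9.4.

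The note in Protocol 3.2 recommends treating both kidneys when both need stenting, so some subjects will have two study lesions. It also covers bilateral subjects with only one qualifying lesion, who contribute one.

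Enrolment "has been terminated after 68 subjects were screened and enrolled in the study" (SAP 6.1). SAP 2, 6.2 and 8.7 therefore make the inference descriptive, without Type I error control.

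**The concern.** Two renal arteries in one patient share blood pressure, drug treatment, operator and underlying disease, so their patency outcomes are likely to be positively correlated. An ordinary logistic regression on lesion records takes every record as independent. All three subgroup factors belong to the subject, so paired lesions always carry the same covariate value. That is the case in which positive correlation makes the model's standard errors too small. In the first contrast listed, the pairs all fall on the bilateral side.

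Exact binomial intervals also assume independent units, so the subgroup intervals of SAP 8.1 have the same weakness wherever a subgroup contains pairs.

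A second and separate matter is the number of failures. After early termination there may be too few for stable maximum-likelihood odds ratios. What is at stake is whether the reported subgroup estimates and their precision can be taken at face value.

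**Working it through.** **The plan's own figure.** The documents give no failure count, standard error or power for the subgroup model. The design figure for patency does reproduce. With 125 evaluable, at most 27 failures (98 or more patent), a goal of 0.70 and a true rate of 0.82, the exact one-sided alpha is 0.0230 and the power 0.876, against the stated 0.025 and 87%.

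**Inputs from the documents**

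- 68 subjects (SAP 6.1).
- Lesions per subject: "A recent renal trial reported 1.2 lesions per subject were treated" (SAP 5.2). This comes from a different trial.
- At most two study lesions per subject. Protocol 3.3 excludes multiple ipsilateral lesions that one stent cannot cover, and SAP 7.6.1 counts a stented segment as one lesion.
- Failure rate f = 1 − 0.82 = 0.18 (SAP 5.5).

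**Assumptions not in the documents**

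- Within-subject correlation rho from 0 to 0.5.
- Alternative failure rates of 10% and 5%.
- At first, every bilateral subject has two treated lesions and nobody is lost.

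**Lesion counts.** 68 × 1.2 = 81.6, about 82 lesions. Two-lesion subjects: 0.2 × 68 = 13.6, about 14. That leaves 54 one-lesion subjects, and 54 + 2 × 14 = 82.

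**Standard error of the log odds ratio.** For 54 unilateral lesions and 28 bilateral lesions:

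SE² = 1/(54·f(1−f)) + (1+rho)/(28·f(1−f)), with f(1−f) = 0.18 × 0.82 = 0.1476.

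At rho = 0, which is what the plain model reports: 0.1255 + 0.2420 = 0.3674, so SE = 0.606.

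| rho | correct SE | ratio to plain SE | actual level of a nominal two-sided 5% test |
|---|---|---|---|
| 0 | 0.606 | 1.00 | 5.0% |
| 0.1 | 0.626 | 1.03 | 5.8% |
| 0.3 | 0.663 | 1.09 | 7.3% |
| 0.5 | 0.699 | 1.15 | 8.9% |

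**Bilateral subjects with one study lesion.** As an illustration, suppose 7 of the 54 one-lesion subjects also have bilateral stenosis. The groups are then 47 and 35 lesions, and the bilateral term becomes (1 + 0.8·rho)/35, because 28 of its 35 lesions are paired. At rho 0.3 the plain SE is √[(1/47 + 1/35)/0.1476] = 0.581 and the correct SE is √[(1/47 + 1.24/35)/0.1476] = 0.620. The ratio is 1.07 instead of 1.09.

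**Small-sample check.** A simulation used 200,000 runs per setting, 54 one-lesion and 14 two-lesion subjects, and no true difference. Means and SDs exclude runs with a zero-failure group; the Wald rate counts such runs as not significant.

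| f | rho | mean plain SE | actual SD | Wald rejects | likelihood-ratio rejects |
|---|---|---|---|---|---|
| 18% | 0.2 | 0.650 | 0.707 | 4.2% | 7.2% |
| 18% | 0.3 | 0.653 | 0.724 | 4.6% | 8.0% |
| 18% | 0.5 | 0.657 | 0.759 | 5.6% | 10.0% |
| 10% | 0.3 | 0.849 | 0.830 | 3.3% | 9.9% |
| 5% | 0.3 | 1.071 | 0.814 | 1.3% | 8.5% |

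**Number of failures.** Among 82 lesions: 82 × 0.18 = 14.8 (28 × 0.18 = 5.0 in two-lesion subjects); 82 × 0.10 = 8.2 (2.8); 82 × 0.05 = 4.1 (1.4). With 10% attrition (61 subjects, 73 lesions), 13.1 are expected at 18%.

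**Chance of a zero-failure group at rho 0.3.** A pair has no failure with probability (1−f)² + rho·f(1−f).

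- f = 18%: 0.717, and 0.717¹⁴ is about 0.9%. The unilateral group adds almost nothing.
- f = 10%: 0.837, and 0.837¹⁴ = 8.3%. Adding 0.9⁵⁴ = 0.3% gives 8.6%.
- f = 5%: 0.917, and 0.917¹⁴ = 29.6%. Combined with 0.95⁵⁴ = 6.3%, this gives 34%.

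The documents give no expected split by gender or age, so the same sums cannot be done for those contrasts.

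**The case against.** The strongest reply is that independence is nowhere stated. SAP 9.9.4 names no unit, and its first contrast is worded in terms of subjects. If the subgroup model follows the count in 9.9.1, each subject gives one outcome and no clustering arises. This stands as a limit: the point is conditional on the lesion being the unit. It does not dispose of the matter, because 7.6.1 and 8.8 say the opposite of 9.9.1 and the passages have to be reconciled anyway.

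The second reply is that nothing depends on 9.9.4. The SAP calls all inference descriptive and makes no success claim from subgroups. That stands, and it keeps the point minor. A descriptive interval should still have roughly its stated coverage, however, and 9.9.4 still asks about significance.

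Third, the exact subgroup intervals in SAP 8.1 stay finite with zero failures, so reporting does not rest on odds ratios alone. This is true, and the conservatism of exact intervals may absorb a small correlation. They are still not adjusted for pairing.

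A reader might also infer that scarce failures make the error bars too narrow. The simulation does not bear this out. At 10% failure and rho 0.3 the plain standard error is about right, and at 5% it is too wide. Even at 18% the Wald test stays near its nominal level, although the likelihood-ratio test over-rejects. Scarcity causes instability and non-finite estimates.

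Another tempting step is to apply √(1+rho), which is 5%, 14% and 22% at rho 0.1, 0.3 and 0.5, to the comparison. That factor applies within the bilateral group only. The unilateral group adds variance that pairing does not affect.

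**Conclusion.** The point holds in a conditional and modest form. If 9.9.4 is run on lesions, a plain logistic regression and unadjusted exact intervals overstate precision whenever outcomes within a subject are positively correlated. For the unilateral-versus-bilateral contrast, the large-sample effect on the standard error is about 3% to 15% over rho 0.1 to 0.5. It is nil at rho 0, and smaller if some bilateral subjects contribute one lesion. The direction is the same for gender and age; the size was not computed. These figures rest on an assumed correlation, on 1.2 lesions per subject borrowed from another trial, and on 18% failure.

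Independently of this, about 15 failures at the planned rate, or about 8 at 10%, leave a real chance of a subgroup with none, and the SAP gives no fallback. This is a worthwhile tidying of the plan. It does not threaten the primary result.

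**What to change.** 1. State in SAP 9.9.4 whether the record is a lesion or a subject, and reconcile 7.6.1 and 8.8 with 9.9.1. Correct the cross-reference in 8.1.
2. If the lesion is the unit, fit the model by GEE or with cluster-robust variance, clustering on subject. Use a small-sample correction, since only about 14 pairs are expected. Replace the exact subgroup intervals with cluster-adjusted ones.
3. Set in advance a minimum number of failures per subgroup for fitting the model. Below it, report only rates with intervals. With zero failures a robust variance is also zero, so an exact interval based on the number of subjects, not lesions, is a safe choice.
4. Drop the search for significance and report estimated differences with confidence intervals, in keeping with the descriptive status in SAP 2 and 6.2.

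The cost is a few lines of text, a little more code and slightly wider intervals. No new data are needed.

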9.9.5. Exploratory Analyses

No exploratory analyses of efficacy data are planned.

9.10 Analysis of Secondary Endpoints

Due to study enrollment termination, the secondary endpoints will not be evaluated using a gatekeeping or hierarchical approach. All secondary analyses will be performed using the ITT analysis population and missing data imputation will not be performed.

9.10.1. TLR

The secondary endpoint of clinically driven TLR will be summarized using counts and frequencies. An exact binomial one-sided 95% confidence interval will be constructed and the upper limit compared to the Performance Goal rate of 8.5%. A p-value for the one-sided test of the difference between the observed rate and the Performance Goal will be presented.

9.10.2. Changes in the number or dosage of antihypertensive medications

The secondary endpoint of changes in the number or dosage of anti-hypertensive medications as compared to baseline will be summarized using continuous summary statistics (n, median, mean, SD, min, max) for the ITT population. The average number of anti-hypertensive medications and dosage will be compared to baseline using the paired t-test.

In addition, the proportion of subjects with changes in the number or dosage of anti-hypertensive medications will be presented by counts and percents for the ITT population.

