### **5.3.4 MULTIPLICITY ADJUSTMENT**

Alpha for the primary hypotheses will be controlled by testing the endpoints hierarchically. Patency will be tested first followed by systolic blood pressure. The test for systolic blood pressure will only be conducted if the patency Performance Goal is met.

Two additional secondary endpoints will be evaluated hierarchically if and only if the primary objective is met. In order to control alpha, the endpoint of clinically driven TLR will be tested as described below, followed by changes in the number or dosage of anti-hypertensive medications as compared to baseline.

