#### 5.3.6.2.1.2 CHANGES IN THE NUMBER OR DOSAGE OF ANTI-HYPERTENSIVE MEDICATIONS

The secondary endpoint of changes in the number or dosage of anti-hypertensive medications as compared to baseline will be summarized using a shift table. The number of patients will be compared to baseline using the paired McNemar's test.

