6.2 Changes from the Analyses Planned in the Protocol/CIP

Due to the early termination of enrollment for Protocol/CIP No. iCAST™ RX-ARAS-001, all inferential analysis should be interpreted as descriptive and will be carried out in an exploratory manner.

The following changes were applied:

1. Missing data will not be imputed.
2. Sensitivity analysis will be limited to evaluating the primary analysis results using the per protocol population.
3. Supportive analysis of the revascularization information using a time to event approach will be performed.

Confidential

7. BASELINE, EFFICACY and SAFETY EVALUATIONS

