A clinically-driven TLR is defined as a target lesion revascularization (PTA, bare metal stent or repeat covered stent deployment, or surgical bypass) due to documented recurrent hypertension from 30-days post-procedure level and/or deterioration in renal function from baseline value, and associated with angiographic core laboratory adjudication of a $\geq 60\%$ diameter covered stent restenosis.

The percentage of TLRs will be derived as the number of subject-lesions that require a clinically-driven re-intervention divided by the number of subject-lesions in the ITT population.

5. Rate of incidental TLR

The rate of TLRs not meeting the definition of a clinically-driven TLR will be derived as the number of observed non-clinically driven TLRs divided by the total number of subject-lesions in the ITT population.

6. Improved SBP control assessed at 30-days, 9-months, 12-months, 24-months and 36-months.

The change from baseline in systolic blood pressure (SBP) at each follow-up time point will be computed as follows:

$$\text{SBP change from baseline} = (\text{SBP value at follow-up} - \text{SBP value at baseline})$$

7. Secondary patency rate at 9-months

Secondary patency rate at 9-months after a clinically-driven TLR which restores patency after total occlusion. For each subject-lesion, an indicator variable will be derived which identifies if the lesion meets secondary patency. The incidence of secondary of patency at 9 months will be computed as the number of subject-lesions that met secondary patency divided by the number of subject-lesions for the ITT population.

Confidential

8. Change in number and dosage of anti-hypertensive medications

Anti-hypertensive medications as well as the dosage will be recorded at baseline and throughout the study follow-up. The total number of anti-hypertensive medications will be computed as the sum of all available anti-hypertensive medications at each time point. Change from baseline will be computed as follows:

Change from baseline in the number of antihypertensive medications = (number of anti-hypertensive medications at follow-up – the number of anti-hypertensive medications at baseline)

Additionally, an indicator variable which detects if an increase in the number of antihypertensive medications (change from baseline > 0) was observed will be derived.

Similarly, the change from baseline in the anti-hypertensive medication dosage (within the same medication) will be computed as follows:

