Change from baseline in the antihypertensive medication dosage = (Dosage of anti-hypertensive medication at follow-up – the dosage of the anti-hypertensive medication at baseline).

An indicator variable which identifies any increases in dosage (change from baseline > 0) will also be derived.

9. Renal function compared to baseline as measured by eGFR at 30-days and 9-months.

Renal function will be assessed by eGFR at the 30-days and 9-months of study follow-up. eGFR results will be estimated by the abbreviated Modification of Diet in Renal Disease(MDRD) equation : $186 \times (\text{Creat} / 88.4) - 1.154 \times (\text{Age}) - 0.203 \times (0.742 \text{ if female}) \times (1.210 \text{ if black})$.

The change from baseline in eGFR will be computed as follows:

Change from baseline in eGFR = (eGFR result at follow-up – eGFR result at baseline)

- i. In addition, an indicator variable will be derived in order to identify decreases from baseline in eGFR of >25%, >40%, >50% at any time point.

Amendment #1: 15Jul13

7.6.3.Safety Outcomes and Other Parameters

The main safety outcome is the incidence of subjects with any adverse event experienced after the study procedure has occurred over the totality of the study.

Other parameters collected to monitor safety and/or to derive efficacy include:

- Vital signs (systolic and diastolic blood pressure)
- Laboratory Assessments (chemistry, urine analysis, proteinuria, eGFR)
- Physical Examination (assessment of general appearance, abdomen, cardiovascular, dermatologic, genitourinary, head, eyes, ear, nose and throat (HEENT), lymph nodes, musculoskeletal, neurological, respiratory)
- Duplex Ultrasound (degree of stenosis)
- Angiography (degree of stenosis)
- Revascularization (number of revascularization, location, type)
- Concomitant medications/antihypertensive medications
- Mortality

8. STATISTICAL METHODS**8.1 General Statistical Considerations**

Data collected in this study will be presented using summary tables and subject data listings.

Demographic, endpoint information, safety data and other parameters will be summarized and presented for the ITT and Per-Protocol populations accordingly. Summaries for continuous and ordinal variables will include the number of observations (n), arithmetic mean, standard deviation (SD), minimum (min), maximum (max), median, and 95% confidence intervals of the means.

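### The SAP replaces the protocol's shift table and McNemar test for antihypertensive drugs with a paired t-test, without listing the change, and the dosage part of that test has no defined value per subject

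*SAP*

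**What the plan says.** - **Protocol 5.3.4** puts this endpoint last in the alpha-controlled sequence, after clinically driven TLR: "followed by changes in the number or dosage of anti-hypertensive medications as compared to baseline".
- **Protocol 5.3.6.2.1.2** says that the changes "as compared to baseline will be summarized using a shift table", and then: "The number of patients will be compared to baseline using the paired McNemar's test".
- **SAP 7.6.2, item 8** defines change in the number of drugs as follow-up minus baseline, with an indicator for an increase. For dose, "the change from baseline in the anti-hypertensive medication dosage (within the same medication) will be computed as follows", again as follow-up minus baseline. It adds: "An indicator variable which identifies any increases in dosage (change from baseline > 0) will also be derived".
- **SAP 9.10.2** plans continuous summaries and the test: "The average number of anti-hypertensive medications and dosage will be compared to baseline using the paired t-test". It adds that "the proportion of subjects with changes in the number or dosage of anti-hypertensive medications will be presented by counts and percents".
- **SAP 9.10.3, item 7** lists the same endpoint among those to be described without a test.
- **SAP 6.2** lists three changes from the protocol analyses: no imputation, sensitivity analysis limited to the per-protocol population, and, as the third, "Supportive analysis of the revascularization information using a time to event approach will be performed". SAP section 2 covers only the exploratory status of the inference and the absence of imputation.

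**The concern.** A planned method has changed and the SAP's own list of changes does not show it. The new method also needs something that the SAP does not supply, namely one dosage number per subject at each time point.

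The endpoint matters because the trial has one arm. A fall in systolic pressure means one thing if subjects are on less medication at 9 months and another if they are on more. Protocol 3.4 bars titration during the screening period, and we find no such bar afterwards, so therapy may move either way during follow-up. A reader of the blood-pressure result needs to know how many subjects moved in each direction.

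**Working it through.** The documents give no alpha, power, effect size or standard deviation for this endpoint, so there is no figure to reproduce. The check compares the texts and adds one illustration.

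**1. Was the change disclosed?** The protocol has a shift table and McNemar's test. The SAP has means, standard deviations and a paired t-test, plus a proportion with changes. None of the three items in SAP 6.2 covers this. SAP 9.10 discloses that the hierarchy was dropped, but not that the test was replaced. Early termination does not explain the switch: a shift table and an exact McNemar test both work with the 68 enrolled subjects (SAP 6.1).

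**2. Is the tested variable defined?** A paired t-test uses one difference d per subject: t = mean(d) / (SD(d)/√n).
- *Number of drugs:* d is the count at follow-up minus the count at baseline. This is defined and interpretable.
- *Dosage:* the entry criteria require at least three drugs of different classes, so drug-by-drug changes give several values of d per subject. The SAP gives no rule for combining them and no common dose unit. SAP 9.10.2 also names no visit.

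There are three ways to proceed, and the SAP describes none of them. Averaging raw doses mixes scales. A separate test per drug splits 68 subjects into small groups. Treating each drug as a row breaks independence within the subject.

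**3. What would pooling raw doses do?** Illustration only; every input except n = 68 is assumed. Each subject takes two drugs whose milligram scales differ by a factor r.
- High-milligram drug: no net change (15% of subjects up by half, 15% down by half). Variance = 0.25 × 0.30 × r² = 0.075r².
- Low-milligram drug: dose halved in 40% of subjects. Mean = −0.5 × 0.4 = −0.2; variance = 0.25 × 0.4 × 0.6 = 0.06.
- Signal-to-noise of the t statistic = √68 × 0.2 / √(0.06 + 0.075r²) = 1.649 / √(0.06 + 0.075r²).

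| r | Signal-to-noise | Rejection on raw mg (simulated, two-sided 0.05) | Rejection on change relative to baseline dose |
|---|---|---|---|
| 1 | 4.49 | 99.6% | about 99% |
| 5 | 1.19 | 21% | about 99% |
| 20 | 0.30 | 5.7% | about 99% |
| 100 | 0.06 | 5.3% | about 99% |

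If raw doses were pooled, the drug with the largest numbers would decide the result.

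**4. Starts, stops and substitutions.** A drug started or stopped after baseline lacks one of its two doses. SAP 7.6.2 does not say that a drug not taken counts as zero, and SAP 8.3 and 9.10 rule out imputation. The drug count picks up net additions and withdrawals. A one-for-one substitution leaves the count unchanged and has no within-drug pair, so it escapes both measures.

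**5. Is direction visible?** Both indicators flag increases only, and the proportion in SAP 9.10.2 pools both directions. If all 68 subjects reduced therapy, or all 68 increased it, that proportion would be 68/68 either way. A mean change of zero in the number of drugs fits 68 unchanged subjects as well as 34 losing a drug and 34 gaining one (68/2 = 34).

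**6. Is the endpoint tested?** SAP 9.10.2 says yes. SAP 9.10.3 is meant for the remaining endpoints, yet its item 7 names this one and says no.

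**The case against.** The strongest reply is that this is a gap of specification in an analysis already declared descriptive (SAP 2, 6.2 and 8.7), with the hierarchy dropped (SAP 9.10). That stands as a limit on the consequences. It does not make the dosage mean computable: an undefined variable is as unclear in a descriptive table as in a test.

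The reply also corrects three stronger readings that a reader might infer.
- *That the SAP averages milligrams across different drugs.* It does not say so; SAP 7.6.2 works drug by drug. The table above therefore shows what one possible reading would do. For the same reason, an example in which swapping a drug swings the mean dose proves nothing: under the drug-by-drug definition the swapped drug has no pair and contributes no change.
- *That reductions are never counted.* Both change variables are signed, so reductions enter the means, and fewer drugs lower the mean count. SAP 9.8 also tabulates antihypertensive use by broad category and visit. For the number of drugs, reductions could be found by subtracting increases from changes if both were tabulated separately, but SAP 9.10.2 does not plan that. For dose, subtraction would miss a subject with one drug up and another down.
- *That McNemar's test was a complete plan.* The protocol does not define the two-state variable that the test needs, so restoring its wording alone would not be enough.

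**Conclusion.** The point holds in a limited form. The protocol's shift table and McNemar test were replaced and the SAP's lists of changes do not say so. The dosage t-test has no defined value per subject. No planned count sets reduced against increased therapy. Two adjacent SAP sections disagree on whether the endpoint is tested.

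The documents do not support calling the whole endpoint uninterpretable, because the number-of-drugs comparison and the individual within-drug changes can be read. They also do not support saying that a success claim is at risk. The endpoint's place in the alpha-controlled sequence is the protocol's, and the SAP has given that up.

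The size cannot be stated from the documents. The range of 99.6% down to 5.3% applies only if raw doses are pooled, and rests on the assumed doses and changes in the illustration. The practical loss is context for the systolic pressure change. The change is worth making because it is cheap and uses data already collected.

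**What to change.** - Drop the paired t-test on dosage.
- Classify each subject at 9 months as reduced, unchanged or increased, separately for number of drugs and for dose. Judge dose against that subject's own baseline dose of the same drug. Count a start as an increase and a stop as a reduction, and show mixed changes and substitutions as their own category.
- Present the shift table that the protocol promised. Compare reduced with increased by an exact sign/McNemar test: with b reduced and c increased, refer b to a binomial distribution with b + c trials and probability 1/2. Label it descriptive.
- Add the change of method to SAP 6.2, and reconcile SAP 9.10.2 with item 7 of SAP 9.10.3, for instance by removing that item.

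The cost is a little more programming and SAP wording, and the loss of a single mean dosage figure. No new data are needed: Protocol 4.6 requires all medications to be recorded, and SAP 7.6.2 says that antihypertensive doses are recorded at baseline and through follow-up.
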